Deviations from this study protocol, or conditions comprising exclusion criteria established in [Section 7.3](#) that arise after the subject has been included in the study may (but will not necessarily) lead to the discontinuation of subject's study participation. All such conditions must be properly documented. Any deviations related to a public health emergency, e.g., due to a COVID-19 outbreak (e.g., visit deviations, remote assessments, rater change due to staff being unavailable in case of a public health emergency) must be documented as such. Subjects who discontinue the study because of AEs will be treated according to standard clinical procedures. For any subject discontinuing the study, the end-of-study visit (V11) should be conducted. All pertinent information concerning the AE will be documented in the source documentation as well as in the eCRF report form until V11. No information will be collected in the eCRF thereafter.

The investigator is required to make every effort to contact subjects lost to follow-up, and all such efforts are to be documented in the source documentation (e.g. times and dates of telephone contact, copies of letters).

Subjects who discontinue the study will not be replaced.

7.5.2 Premature termination or suspension of the study or closure/suspension of a study site

The study or a study site can be prematurely terminated or suspended by the sponsor. Reasons for termination of the study or closure of a study site may include, but are not limited to, the following:

- Subject enrollment is unsatisfactory;
- The risks and benefits of continuing the study have been reassessed, and the risks outweigh any potential benefits;
- The incidence of AEs constitutes a potential health hazard to the subjects;
- New scientific data on the IP(s) do not justify a continuation of the study;
- The investigator or study site exhibits serious and/or persistent non-adherence to the clinical study protocol, the Declaration of Helsinki, ICH-GCP, and/or applicable regulatory requirements; and
- The sponsor decides to terminate or suspend the study at any time for any other reason. The study may be prematurely ended if the regulatory authority or the IEC/IRB has decided to withdraw or suspend approval for the study, the study site, or the investigator.

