In case of premature discontinuation from the study, the procedures of the end-of-study visit (V11) will be conducted at the subject's last visit, if possible. If additional safety follow-up is necessary after this assessment, i.e., for SAEs ongoing at the time of V11, subjects may be contacted by telephone or assessed in the clinic, depending on the nature of the follow-up required.

In case of a public health emergency, e.g. due to a COVID-19 outbreak the study might be put on hold, recruitment interrupted, and/or study processes and flow might be modified with impact to the study duration/visit schedule depending on the current study status (see [Section 7.4.1](#) and [Section 9.1.1](#)). In case of such a public health emergency the study procedures foresee the following implications for visit performance by subjects:

- Any modifications to visits and visit activities need to be documented accordingly (see [Section 11.2](#)). For example, visits performed outside the visit window because of such events must to be documented as such.
- Subjects having completed screening visit V1 and not received study medication due to any of such an event must perform a rescreening if a delay in planned activities occurred and study activities at site are possible again (see allowance of one rescreening for a subject described above in this [Section 9.2](#)).
- Investigators and subjects can decide to replace on-site visits V3-V8 of Cycle 1 or V9 – V11 of Cycle 2 with a remote visit (e.g. by phone call) (see [Section 9.1.1](#) and [Table 5](#) and [Table 6](#) below).
- If in case the end-of-Cycle 1 visit (V8) had to be conducted as a remote visit (e.g. by phone call), the Cycle 2 open-label bilateral treatment period will be postponed until on-site activities are possible again (see also [Section 7.4.1](#)).
- In case study visits for subjects in Cycle 1 were put on hold or in any way modified so that V8 of Cycle 2 could not be performed according to study plan (e.g. more than 25 weeks after Cycle 1 injection at baseline visit V2), subjects will not perform V8 of Cycle 2 but will continue the study with V8a of Cycle 2 on site when this is possible again (see [Section 7.4.1](#), [Table 5](#), and [Table 6](#) below).

Table 5: Visit schedule during the double-blind unilateral treatment period

M602011069	Screening	Cycle 1: Double-blind unilateral treatment period						
	Screening visit	Study baseline visit	Control visits					End-of-Cycle 1 visit

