- Absolute values of HHD grip strength testing and changes from applicable cycle baseline to all applicable post-baseline visits will be summarized descriptively by treated UL. In addition, for the unilateral phase the intra-individual difference of changes from baseline between body sides will be summarized;

- 

- Time courses of vital signs (blood pressure, pulse rate) and body weight measurement at selected visits and changes from applicable cycle baseline will be summarized descriptively; and
- Time courses of standard clinical chemistry and hematology parameters measurement at selected visits and changes from applicable cycle baseline will be summarized descriptively.

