2.2.2.3 Other Safety Endpoints

- Exposure to study treatment (including injected volume [mL], number of injection points) by muscle and treated UL for both study periods
- Incidence of TEAEs, TEAEs of special interest (TEAESIs), serious TEAEs, TEAEs leading to discontinuation, COVID-19 related TEAEs for both study periods.
- Time course (i.e., absolute values and changes from study baseline⁵) during the unilateral treatment period (Cycle 1) in Handheld Dynamometer (HHD) maximum grip strength (in hand of injected UL) [Newton] and in maximum grip strength difference between both hands [Newton].
- Time course (i.e., absolute values and changes from Cycle 2 baseline) during the bilateral treatment period (Cycle 2) in HHD maximum grip strength in both hands, by hand of motor-dominant/non-dominant UL [Newton].
- [REDACTED]
- [REDACTED]
- Global assessment of tolerability scale as assessed at Week 24 (V8) of unilateral treatment period and at Week 12 (V11) of bilateral treatment period.

⁵ Wording in CSP Section 12.4.5.2 was "changes from applicable cycle baseline". For consistency, "Cycle 1 baseline" is referred to as "study baseline" everywhere in this document. This does not constitute a change in planned analyses.

- Time course of vital signs (blood pressure, pulse rate) measurement (absolute values and changes from study baseline) during both study periods.
- Time course of body weight measurement and BMI (absolute values and changes from study baseline) during both study periods.
- Time course of standard clinical chemistry and hematology parameter measurements (absolute values and changes from study baseline) during both study periods.
- Time course of suicidality assessment during both study periods.

For definition of study baseline and Cycle 2 baseline see Section 4.

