4.5 Safety Analyses

All safety analyses for Cycle 1 will be performed by actual treatment group on SES-UP. All safety analyses for Cycle 2 will be performed on the SES-BT, by actual treatment group in Cycle 1 and in total. All safety analyses for the total observation period will be performed on SES-UP, by actual treatment group in Cycle 1 and in total.

For calculation of TEAE based incidence rates, the denominator will be the number of subjects in the respective analysis set, by actual treatment group or in total (as applicable).

AEs will be coded according to the Medical Dictionary for Regulatory Activities [MedDRA] version that is in effect at the time the database is closed.

Only TEAEs will be analyzed, which are defined as AEs with onset or worsening after the first administration of the IP. For details on separation of TEAEs and non-TEAEs see [Appendix 8.5](#).

If in case of a public health emergency, e.g. due to a COVID-19 outbreak, the second injection visit V8a of Cycle 2 is performed later than 25 weeks after the first injection visit V2 the AEs

¹⁷ Health state = pattern of scores over the five dimensions, e.g., 13333 for a subject indicating slight problems in mobility and severe problems on the other four dimensions.

starting or worsening later than 25 weeks after baseline visit V2 of Cycle 1 and before injection at V8a of Cycle 2 are treated as non-TEAEs.

If an AE worsens between start and end of this AE, it will be considered as new AE entry with a new record in the SDTM dataset starting with the date of the worsening (start of new AE = worsening date, stop date of milder AE episode = date of AE worsening).

For analysis, incompletely recorded or completely missing start of AEs will be estimated according to rules laid down in [Appendix 8.6](#). End dates will not be imputed. In the AE listing, start date as recorded and as imputed for analysis will be displayed.

Calculation of time to onset/duration of AEs (days):

- Time to onset of an AE is defined as start date of AE - date of first administration of study drug in respective treatment cycle [+ 1 day for TEAEs]
- The duration of an AE will be calculated as stop date - onset date + 1 day. The duration of an AE will be missing if no AE stop date is provided

Treatment-relatedness of AEs will be determined based on the assessment of the investigator.

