 - For Cycle 2, maximum grip strength will be summarized separately for motor dominant and non-dominant UL. In case, deviation from CSP, not all subjects in the SES-BP were treated at both ULs, the analyses will be performed on the subset of subjects treated at the respective UL in Cycle 2 and an explanation (including Subject ID, treatment group, untreated UL [motor dominant or non-dominant] of affected subjects) will be provided in a footnote. In case either or both UL are erroneously not injected in Cycle 2, respective values and changes will only be listed.

- [REDACTED]
- [REDACTED]
- [REDACTED]
- [REDACTED]
- [REDACTED]

- Global assessment of tolerability as assessed at Week 24 of unilateral treatment period will be summarized descriptively by treatment group. Week 12 of bilateral treatment period will be summarized descriptively by treatment group and overall. This includes frequency tables and descriptive statistics for metric variables.
- Time course of vital signs (blood pressure, pulse rate), body weight measurement and BMI at selected visits (values and changes from study baseline in both injection cycles) will be summarized descriptively;
- Time course of standard clinical chemistry and hematology parameters measurements at selected visits (values and changes from study baseline in both injection cycles) will be summarized descriptively.

Laboratory values from Screening Visit V1 will serve as study baseline. In case laboratory testing scheduled for Screening Visit V1 was performed after V1 but before Baseline Visit V2 (treatment visit), these values will be analyzed as study baseline. I.e., in line with definition of study baseline provided at beginning of Section 4, baseline flag is 'yes' for last record with non-missing value before first treatment in SDTM). The first valid value is analyzed for a post baseline visit. In addition to descriptive statistics, shift tables from study baseline to Week 24 (V8) and from study baseline to EOS (V11) will be provided.

In case no exact value is given because a laboratory value is below limit of detection and thus provided as <x.x, the respective value (x.x) will be used for calculation of descriptive statistics for metric variables, and <x.x will be listed and flagged accordingly.

- Other safety data will be listed only.

For definition of study baseline and Cycle 2 baseline see beginning of Section 4.

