4.7.4 Premature discontinuations of study participation

Premature discontinuation of study participation and main reason for discontinuation will be analyzed descriptively (see Section 4.6.1). If premature discontinuation is related to a public health emergency, e.g. due to a COVID-19 outbreak, this information will be documented and listed. Incidence of TEAEs leading to study discontinuation (in total and related to treatment), if any, will be reported as part of the overall summary on TEAEs; details of respective TEAEs will be listed by subject (see Section 4.5.3). Discontinued subjects will generally not be replaced.

For subjects discontinuing the study prematurely and for whom EOS visit V11 was documented,

efficacy endpoints based on TETRAS ADL or TETRAS Performance assessments or kinematic tremor assessment with TremorTek performed at V11 will be analyzed under the study visit which is closest to the recorded V11 date. This will be based on the assessment date relative to study / Cycle 2 baseline, and considering treatment received for each cycle, using adapted visit windows as displayed in [Table 2](#).

Table 2: Adapted Visit Windows for Assignment of V11 to Analysis Visit for subjects prematurely discontinuing the study

| Analysis visit | Window Start Day | Window End Day | Window(s) applicable for |
|----------------|------------------|------------------------|--|
| Week 4 (V3) | 2 | 35 | all subjects ¹ |
| Week 6 (V4) | 36 | 49 | |
| Week 8 (V5) | 50 | 70 | |
| Week 12 (V6) | 71 | 105 | |
| Week 18 (V7) | 108 | 147 | |
| Week 24 (V8) | 148 | Open end | subjects ¹ not treated in Cycle 2 |
| Week 24 (V8) | 148 | Day of treatment in C2 | subjects ¹ treated in Cycle 2 |
| Week 4 (V9) | C2 / Day 2 | C2 / Day 35 | |
| Week 6 (V10) | C2 / Day 36 | C2 / Day 63 | |
| Week 12 (V11) | C2 / Day 64 | Open end | |

¹ subjects prematurely discontinuing the study

Note that V11 EOS data will never be assigned to any (cycle) baseline visit based on the above rules.

In general, if based on the above windows, a V11 EOS assessment would be assigned to a timepoint for which a regular visit was performed and respective TETRAS ADL/ TETRAS Performance / kinematic tremor assessments are available, then the respective data from the regularly performed visit will be used for analysis, and V11 data will only be listed.

All other data collected at EOS visit (V11) will generally be analyzed at V11.

5 Sample Size Determination

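### Cycle 2 changes in vital signs, weight and laboratory values are measured from study baseline, contrary to the protocol, and early-termination V11 values other than tremor data have no correct place in the by-cycle tables

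*SAP*

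**What the plan says.** **Baseline for change.** Protocol 12.4.5.3 states for vital signs and weight: "body weight measurement at selected visits and changes from applicable cycle baseline will be summarized descriptively". It uses the same baseline for clinical chemistry and hematology. SAP 4.5.3 has, for vital signs, weight and BMI and again for laboratory data: "values and changes from study baseline in both injection cycles) will be summarized descriptively". SAP 2.2.2.3 agrees with SAP 4.5.3. Footnote 5 of that section is attached to Cycle 1 grip strength. It explains that Cycle 1 baseline is renamed study baseline and adds: "This does not constitute a change in planned analyses". SAP Section 6 lists the departures from the protocol, and this one is not among them.

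**Termination visit.** Protocol 7.5.1: "For any subject discontinuing the study, the end-of-study visit (V11) should be conducted". Protocol 9.2 repeats this. SAP 4.7.4 says that TETRAS and TremorTek data from such a visit "performed at V11 will be analyzed under the study visit which is closest to the recorded V11 date", using the windows of SAP Table 2. For everything else: "All other data collected at EOS visit (V11) will generally be analyzed at V11".

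**Analysis sets.** SAP 4.5: "All safety analyses for Cycle 2 will be performed on the SES-BT, by actual treatment group in Cycle 1 and in total". SES-BT is not defined and must mean SES-BP, the subjects injected in Cycle 2. Cycle 2 efficacy tables, including QUEST, use FAS-BP, which is a subset of SES-BP.

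**The concern.** Safety of bilateral treatment is a stated secondary objective. A Cycle 2 table that shows change since the start of the study does not isolate what followed the bilateral injection, and the protocol promised the change that would. Section 12 of the protocol requires deviations from planned analyses to be described in an amendment or in the SAP, so an unlisted change of baseline is also a gap in traceability.

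The termination visit matters because subjects who stop early may differ from those who stay. If the last record of a subject who stops in Cycle 1 has no row in a Cycle 1 table and the subject is barred from Cycle 2 tables, the summaries describe only those who remained. If a subject stops soon after the bilateral injection, the values appear under a timepoint the subject never reached.

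**Working it through.** The plan has no figure of its own for this point. Its sample-size figure (51 analysable subjects) does not enter. The check is a trace of the rules, with illustrations marked as assumptions.

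**1. What the Cycle 2 change contains.** For any Cycle 2 visit:

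change from study baseline = (Cycle 2 baseline − study baseline) + (visit − Cycle 2 baseline).

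The first bracket is the whole of Cycle 1. At V11 the span is 24 + 12 = 36 weeks, against 12 weeks from Cycle 2 baseline. For laboratory data, study baseline is the screening sample (SAP 4.5.3), taken up to 3 weeks earlier, so the span reaches 39 weeks. It is longer still if Cycle 2 was delayed to V8a.

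**2. Effect on the total column.** Let d be the mean change from study baseline to Cycle 2 baseline in each Cycle 1 arm. With the arms in SES-BP at 2:1, the total column differs from the true Cycle 2 change by (2 × d_NT201 + d_placebo)/3. Assumed values: d_placebo = 0, d_NT201 = −2 or −4 units, and a Cycle 2 change of −4 in both arms.

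| d_NT201 | Total, from study baseline | Total, from Cycle 2 baseline |
|---|---|---|
| −2 | (2 × (−6) + (−4))/3 = −5.3 | −4.0 |
| −4 | (2 × (−8) + (−4))/3 = −6.7 | −4.0 |

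If d is zero in both arms, nothing is distorted. The documents give no value for d.

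**3. Which variables are affected.**

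| Variable | SAP baseline for Cycle 2 changes | Matches protocol? |
|---|---|---|
| Vital signs, weight, laboratory | Study baseline | No |
| BMI | Study baseline | Added by the SAP |
| Grip strength | Cycle 2 baseline | Yes |
| QUEST | Both baselines | Yes |

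**4. Where a Cycle 1 termination visit goes.** By SAP Table 2, V11 on day 28, 42, 56, 84, 126 or 168 sends TETRAS and TremorTek data to V3, V4, V5, V6, V7 or V8. Grip strength, QUEST, vital signs, weight, laboratory data and tolerability go to V11 in every case. V11 is not a Cycle 1 visit, and the subject is in neither SES-BP nor FAS-BP. The values therefore enter no by-cycle visit summary. The laboratory shift table from study baseline to EOS (V11) is a possible exception, because SAP 4.5.3 does not name its analysis set. On SES-UP it would combine early stops after unilateral treatment with Week 12 values after bilateral treatment. On SES-BP it would omit the Cycle 1 stops.

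**5. How much of the record this is.** From Protocol Table 5, post-injection assessments in Cycle 1 are scheduled as follows.

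- Vital signs: every visit.
- Grip strength: V3 to V6 and V8.
- QUEST: V4 and V8.
- Weight, laboratory data and tolerability: V8 only.

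For the first three, earlier scheduled visits stay in the tables. For the last group, a subject who stops before V8 normally has no other post-injection record. Protocol 9.1.2 allows extra laboratory tests during an adverse event, but their results are not entered in the study database.

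**6. Early stop in Cycle 2.** A termination visit on Cycle 2 day 21 places tremor data at Week 4 (V9) under Table 2 and all other data at EOS Week 12 (V11). One visit gets two timepoints in the same report.

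**7. Number of subjects.** No discontinuation rate is given. Assuming 5%, 10%, 15% or 20% of 75 stop in Cycle 1, the count is 3.75, 7.5, 11.25 or 15, so about 4 to 15 subjects.

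**The case against.** The affected outputs are descriptive, and the primary and key secondary tests do not use them. This stands.

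SAP Section 4 provides a Cycle 2 baseline row in the Cycle 2 tables for laboratory data, vital signs, weight and BMI, and safety results are also shown by Cycle 1 arm. A reader can subtract means and look at the placebo-first column. This softens the baseline point. It gives only an approximate mean change when some subjects lack the later visit, and no spread or extremes of the within-subject change.

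TETRAS and TremorTek are assessed at every post-baseline visit, so windowing suits them. Applying Table 2 to everything would create Week 4 or Week 18 rows for laboratory data or tolerability, filled only by subjects who stopped. The word *generally* in SAP 4.7.4 also leaves room for exceptions. The first part stands against a blanket use of Table 2, but it does not justify giving these values no row at all.

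A reader might infer three stronger things that the documents do not support.

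- *That all Cycle 2 safety changes use study baseline.* Grip strength, the objective measure closest to hand weakness, does not.
- *That Cycle 1 termination values contaminate the Cycle 2 by-visit tables.* The analysis sets exclude those subjects, so the values are lost, not mixed in.
- *That a loss of grip strength is hidden by a calculable number of newtons.* The documents give no discontinuation rate and no grip values for those who stop. SAP 4.1.2.1 reports that both key secondary endpoints were complete for all treated subjects, so each has TETRAS data for Week 6, either from V4 itself or from a V11 visit on days 36 to 49. Stopping before that window is thus not a source of loss. Muscular weakness is also an adverse event of special interest asked about at each visit from V2, and TEAEs are assigned to cycles by date whatever happens to V11.

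**Conclusion.** The point holds in two limited parts.

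- **Baseline.** For vital signs, weight and laboratory data the SAP departs from the protocol without recording it, and footnote 5 does not cover the departure. BMI follows the same rule. Cycle 2 changes carry whatever happened in Cycle 1, and the total column pools subjects with one and with two NT 201 treatments. The SAP generally avoids such pooling of study-baseline changes for efficacy (SAP 4.1) but not for safety.
- **Termination visit.** Values other than TETRAS and TremorTek are missing from the by-cycle visit summaries for Cycle 1 stops and mislabelled in time for early Cycle 2 stops. The effect is greatest for laboratory data, weight and tolerability.

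The size depends on two quantities the documents do not give: the mean change over Cycle 1 and the number who stop early. One caveat applies. The SAP also cites amendment 1 to protocol version 3.0 (26-MAY-2023), and the protocol text reviewed does not identify itself as including it. Footnote 5, written after that amendment, still cites the cycle-baseline wording as the protocol's.

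**What to change.** 1. In Cycle 2 tables, report changes in vital signs, weight, BMI and laboratory values from Cycle 2 baseline (V8 or V8a). Keep change from study baseline as an extra column, preferably by Cycle 1 arm only. If study baseline is to remain the sole reference, record and justify that in SAP Section 6.
2. In SAP 4.7.4, assign all early-termination V11 data to the correct cycle by date. Use the Table 2 window only where the assessment is scheduled at that visit. Otherwise place the value in a row for last value or early termination in that cycle. Since Table 2 would be reused, close its gap at days 106 and 107 (the V6 window ends on day 105 and the V7 window starts on day 108).
3. Name the analysis set for the laboratory shift table to EOS (V11).

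The cost is SAP wording, some extra columns and rows, and an extension of a mapping already specified for tremor data. No new data are needed, because the V8 and V8a values are already in the visit schedule.

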2.4 Other Data

- Important protocol deviations (PDs), PDs⁶ and other events related to COVID-19 pandemic
- Reasons for exclusion of subjects from analysis sets

3 Analysis Sets

The following analysis sets are defined for the statistical analysis of this study:

Safety evaluation sets

The Safety evaluation set for the unilateral treatment period (SES-UP) includes all subjects who received NT 201 or placebo during the unilateral treatment period.

The Safety evaluation set for the bilateral treatment period (SES-BP) includes all subjects who received NT 201 during the bilateral treatment period.

Full analysis sets

The Full analysis set for the unilateral treatment period (FAS-UP) is the subset of subjects in the SES-UP for whom at least one score of tremor amplitude at wrist level (injected motor-dominant UL) at study baseline and at least at one post-baseline score (V3 to V8) during the unilateral treatment period are available.

For definition of study baseline see Section 4.

The Full analysis set for the bilateral treatment period (FAS-BP) is the subset of subjects in the SES-BP for whom at least one score of tremor amplitude at wrist level at Cycle 2 baseline visit and at least at one post-baseline score (V9 to V11) of both arms during the bilateral treatment period are available.

For definition of study baseline see Section 4.

Per protocol set

The Per protocol set (PPS) is the subset of subjects in the FAS-UP without major PDs. Major PDs will be defined during the blinded data review meeting.

In any analyses on randomized subjects, the FAS-UP, FAS-BP, and the PPS, subjects will be included according to the randomized treatment group. In any analyses on the SES-UP and SES-BP, subjects will be included according to the actual treatment in Cycle 1.

4 Statistical Analyses

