The variable label "treatment group" will be abbreviated with "treatment" in tables, figures, and listings. For analyses of Cycle 1 and Cycle 2 data by treatment group, labels "C1 NT 201" and "C1 Placebo" will be used in respective tables. For analyses by visit the following naming convention will be used: Screening (V1), Study baseline (with "(V2)" for visit attendance table), Week 4 (V3), Week 6 (V4), Week 8 (V5), Week 12 (V6), Week 18 (V7), Week 24 (V8), Cycle 2 baseline (with "(V8(a))" for visit attendance table, tables displaying summary statistics for laboratory data, vital signs, body weight, and BMI in Cycle 2), Week 4 (V9), Week 6 (V10), EOS Week 12 (V11) (without "EOS" in visit attendance table and for efficacy endpoints based on TETRAS ADL or TETRAS Performance assessments or kinematic tremor assessment with the TremorTek® device). For subjects treated at V8, data recorded at V8 will be analyzed as "Week 24 (V8)" and as "Cycle 2 baseline". For subjects treated at V8a, V8 data will be analyzed as "Week 24 (V8)" and V8a data as "Cycle 2 baseline". For subjects discontinuing the study prior to the last scheduled visit at Week 12 in Cycle 2, efficacy endpoints based on TETRAS ADL or TETRAS Performance assessments or kinematic tremor assessment with TremorTek performed at their EOS visit (V11) will be analyzed under the study visit which is closest to the recorded V11 date. Details are described in Section 4.7.4. All other data collected at EOS visit (V11) will generally be analyzed at V11. Except of listing "Visit dates and premature study discontinuation" and listings of violation/ nonfulfillment of re-injection eligibility criteria, Visit V8 and V8a will be listed as "V8(a)". In listing "Visit dates and premature study discontinuation", the following long labels will be used for these two visits: "Week 24 (V8)" and "Cycle 2 baseline (V8a)". Label "EOS Week 12 (V11)" will be used in listings "Important dates" and "Visit dates and premature study discontinuation".

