 - Overall summary of TEAEs, displaying incidences of TEAEs (in total / related to treatment), TEAEs (in total / related to treatment), serious TEAEs (in total / related

- to treatment, TEAEs leading to premature study discontinuation (in total / related to treatment), fatal TEAE (in total / related to treatment) and TEAEs related to COVID-19
- TEAEs, subjects with TEAEs and number of TEAEs by MedDRA SOC and PT
 - TEAEs, subjects with TEAEs by PT
 - TEAEs by worst intensity, subjects with TEAEs
 - TEAEs by worst causal relationship, subjects with TEAEs
 - TEAEs by worst outcome, subjects with TEAEs
 - Serious TEAEs, subjects with serious TEAEs and number of serious TEAEs by SOC and PT
 - Non-serious TEAEs, subjects with non-serious TEAEs and number of non-serious TEAEs by SOC and PT
 - Treatment-related non-serious TEAEs
 - TEAESIs, subjects with TEAESIs and number of TEAESIs by SOC and PT
 - Treatment-related TEAESIs
 - The following by-subject listings of TEAEs occurring in the total observation period will be generated for Section 14.3 of the CSR and include information on treatment cycle:
 - Serious TEAEs, listing of subjects
 - Deaths, listing of all serious TEAEs leading to death
 - TEAEs leading to premature study discontinuation of study, listing of subjects
 - TEAEs of special interest, listing of subjects
 - TEAEs related to COVID-19, listing of subjects.
 - In addition, a complete listing of all AEs (TEAEs and non-TEAEs) occurring in the total observation period will be provided for CSR Section 16.2, also including information on treatment cycle for TEAEs.
- HHD maximum grip strength: Descriptive statistics for HHD maximum grip strength [Newton] (values and changes from applicable cycle baseline, i.e., study baseline for Cycle 1, Cycle 2 baseline for Cycle 2) will be provided by visit for both injection cycles.
 - For Cycle 1, the above-specified analyses will be performed only for treated UL, irrespective of whether the motor dominant UL (acc. to CSP) or the non-dominant UL was treated. Data for non-injected UL will be listed. Furthermore, the intra-individual difference of changes in maximum grip strength from study baseline between hand of treated and hand of untreated UL will be analyzed. The difference will be derived as change from study baseline at hand of injected UL – change from study baseline at hand of non-injected UL.

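### Early Cycle 2 grip-strength values are summarised in the V11 row while tremor data from the same visit are assigned by window, and SAP Table 2 gives Days 106-107 to no visit

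*SAP*

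**What the plan says.** Protocol 7.5.1 and 9.2 ask that a subject who stops early has the V11 procedures, if possible. Protocol Table 6 includes grip strength among them, and also schedules it at V9 and V10.

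SAP 4.7.4 sets two rules for data from such a visit:

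- For the TETRAS subscales and the device data: "kinematic tremor assessment with TremorTek performed at V11 will be analyzed under the study visit which is closest to the recorded V11 date". Table 2 turns this into day windows. A tie rule applies: if the assigned visit already has a regular assessment, that one is analysed and the V11 data are only listed.
- For the rest: "All other data collected at EOS visit (V11) will generally be analyzed at V11". The opening text of SAP Section 4 repeats this.

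SAP 4.5.3 says that grip-strength statistics "will be provided by visit for both injection cycles". The naming convention in SAP Section 4 labels the last visit EOS Week 12 (V11) and drops the EOS prefix only "in visit attendance table and for efficacy endpoints based on TETRAS ADL or TETRAS Performance assessments or kinematic tremor assessment with the TremorTek" device. The grip row therefore keeps the full label.

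In Table 2 the Week 12 (V6) window ends at Day 105, and the next row reads "Week 18 (V7) | 108 | 147".

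**The concern.** Grip strength is reported as a time course, so each row should hold values from about the same time after injection. Under the default rule, a Cycle 2 reading from C2 Day 30 is pooled with true Week 12 readings, while tremor data from the same visit are handled under Week 4. The SAP gives no reason for treating the two differently.

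Hand weakness was the main dose-dependent adverse effect in the larger earlier trial described in Protocol 4.1.2, and Protocol 4.3 reports mild finger weakness in the sponsor's predecessor study. Cycle 2 is the first bilateral exposure. Protocol 6.2 justifies its 12-week follow-up as long enough to see safety past the peak effect. Early readings mixed into that row blur the time point it is meant to show.

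The Table 2 gap is a separate slip. A program written from the table would give a tremor record from Day 106 or 107 no analysis visit, against the sentence that the table implements.

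**Working it through.** **1. Check of the Table 2 boundaries.** Inputs: nominal Cycle 1 days 28, 42, 56, 84, 126 and 168 (Protocol Table 5); Cycle 2 Weeks 4, 6 and 12, i.e. Days 28, 42 and 84 (Protocol Table 6); window limits from SAP Table 2. A closest-visit rule puts each boundary at the midpoint of adjacent nominal days. Unassigned days = next start - window end - 1.

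| Boundary | Midpoint | Window end | Next start | Unassigned days |
|---|---|---|---|---|
| V3/V4 | (28+42)/2 = 35 | 35 | 36 | 0 |
| V4/V5 | (42+56)/2 = 49 | 49 | 50 | 0 |
| V5/V6 | (56+84)/2 = 70 | 70 | 71 | 0 |
| V6/V7 | (84+126)/2 = 105 | 105 | 108 | 108-105-1 = 2 |
| V7/V8 | (126+168)/2 = 147 | 147 | 148 | 0 |
| V9/V10 (Cycle 2) | (28+42)/2 = 35 | 35 | 36 | 0 |
| V10/V11 (Cycle 2) | (42+84)/2 = 63 | 63 | 64 | 0 |

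All seven window ends equal the midpoints. Six of the seven following windows start on the next day; only Week 18 does not. Day 106 is 106-84 = 22 days from V6 and 126-106 = 20 from V7. Day 107 is 23 and 19 days away. Both are closer to V7, so the Week 18 window should start at Day 106.

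**2. Where an early Cycle 2 grip value goes.**

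- As written: any end-of-study grip value goes to the V11 row, whatever its day.
- With the Table 2 windows: C2 Days 2-35 go to Week 4, Days 36-63 to Week 6, and Day 64 onward to Week 12.

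The two rules differ for C2 Days 2-63. All three Cycle 2 windows belong to visits at which grip is scheduled.

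**3. What the tie rule does.** If V9 took place on Day 28 and V10 on Day 42, an end-of-study grip value from Days 29-35 or 43-63 meets an existing regular value and would only be listed. If V9 was missed, a value from Days 2-35 would fill the Week 4 row. If V10 had not taken place, a value from Days 36-63 would fill the Week 6 row.

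**4. Cycle 1.** Protocol Table 5 schedules grip at V3 to V6 and V8, but not at V7. An end-of-study value in the Week 18 window has no grip row to join and needs its own rule.

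**5. Size.** If k Cycle 2 leavers contribute a grip value from C2 Days 2-63 and the V11 row holds N values, the affected share is k/N. The documents give neither number. Assuming N = 70 in total, k = 0, 1, 2 and 4 give 0%, 1.4%, 2.9% and 5.7%. Assuming N = 22 for the former-placebo column, k = 1 and 2 give 4.5% and 9.1%. The shift in the row mean cannot be sized, because grip is summarised in Newtons and the readable text gives no expected values for it.

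**The case against.** The best defence is that the rule is deliberate and disclosed. It is stated twice, the word generally allows exceptions, and the EOS prefix is kept for exactly the data that stay at the end-of-study visit. Keeping such data together suits laboratory values, which the SAP also shows as shifts from baseline to end of study. Part of this stands: the rule is open and reasonable as a default. But no exception is named, and the label still says Week 12.

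A second objection is that the tie rule limits the benefit. For visits on nominal days, values from C2 Days 29-35 and 43-63 would move from a summary to a listing. That is correct and should be accepted: the reading leaves a row where it does not belong, and the subject keeps the regular value at the nearest visit.

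Third, the Days 106-107 gap looks like a one-digit slip, and a misread digit in the public copy cannot be excluded. The governing sentence already resolves it. This limits its weight but does not remove the need to align the table.

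A reader might also infer that a Cycle 1 leaver's last grip reading and only tolerability rating vanish from every table. Cycle 1 tolerability is tied to one visit ("Global assessment of tolerability as assessed at Week 24 of unilateral treatment period will be summarized descriptively by treatment group"), V11 is a Cycle 2 visit, and SAP 4.5 states "All safety analyses for Cycle 2 will be performed on the SES-BT, by actual treatment group in Cycle 1 and in total" (evidently SES-BP, which "includes all subjects who received NT 201 during the bilateral treatment period"). But this is inference. SAP 1.1 places the table layouts in a separate specification, and SAP 4.5 bases safety analyses of the total observation period on the SES-UP. The tolerability rows also follow the protocol's own definition.

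**Conclusion.** Both points hold as small corrections to the text as written. An early Cycle 2 grip value from C2 Days 2-63 is placed in a row labelled Week 12, and Table 2 conflicts with its own closest-visit sentence on Days 106-107.

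The consequences are limited to the descriptive other-safety tables and, for the two-day gap, to the tremor time courses. They depend on the number of early leavers, which is not given and is probably small. SAP 4.1.2.1 reports both Week 6 key secondary endpoints complete for all treated subjects, which in practice rules out Cycle 1 leavers before about Day 36. With no early leavers the effect is zero.

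The documents do not support a stronger reading. The Week 6 window (Days 36-49) is contiguous with its neighbours, so the gap cannot reach the primary or key secondary endpoints. Adverse-event tables keep full denominators, and muscular weakness is actively questioned at each visit as an event of special interest. Nothing shows that the grip summary would be materially distorted. The row shares rest on assumed counts, and the number of calendar days affected says nothing about how many values are. The Cycle 1 grip and tolerability question should be confirmed against the table specification before it is called an error.

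**What to change.** In SAP 4.7.4:

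1. Add handheld-dynamometer grip strength to the data assigned by Table 2, with the existing tie rule. State that an end-of-study value is only listed when the assigned visit already has a regular one. List, or show under a separate label, an end-of-study grip value that falls in the Week 18 window, where grip is not scheduled.
2. Start the Week 18 (V7) window at Day 106.

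Also check in the table specification where a Cycle 1 leaver's end-of-study grip and tolerability values appear. An extra labelled tolerability line for those subjects is optional.

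The cost is a short wording change and one corrected number, with matching table programming. No new data are needed, and no visit changes.
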